7.3.1 Primary Efficacy Analyses

The primary efficacy analysis is to evaluate the time to first relapse of any mood episode in bipolar I disorder patients who responded to OL treatment with cariprazine.

The primary null hypothesis is that the distribution of the time to first relapse for each of the cariprazine 3.0 mg/d and 1.5 mg/d treatment groups is not different from that for the placebo treatment group. The alternative primary hypothesis is that the distribution of the time to first relapse for each of the cariprazine 3.0 mg/d and 1.5 mg/d treatment group is different from that for the placebo treatment group.

The hypothesis testing will compare the time to relapse between each cariprazine group and placebo group using the log-rank test stratified by modified index episode (manic or depressive) for the DB ITT population. To derive the modified index episode, the manic index episode(s) with or without mixed features will be classified as manic episode(s); depressive index episode(s) with or without mixed features will be classified as depressive episode(s). Estimates of the hazard ratio (HR) and 95% confidence intervals will be based on the Cox proportional hazards model with treatment group as covariates stratified by modified index episode (manic or depressive). The Kaplan-Meier estimates for the cumulative distribution of the relapse rate for each treatment group will be provided.

The primary hypotheses for cariprazine 3.0 mg/d and 1.5 mg/d treatment groups versus placebo will be tested sequentially in order to control the overall Type I error rate. The comparison of cariprazine 3.0 mg/d versus placebo will be tested first at the two-sided 0.05 significance level, only when it is significant, the comparison of cariprazine 1.5 mg/d versus placebo will be tested also at the two-sided 0.05 significance level. This testing strategy controls the overall Type I error rate at the 0.05 significance level.

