The hypothesis testing will compare the time to relapse between each cariprazine group and placebo group using the log-rank test stratified by modified index episode (manic or depressive) and region (US, non-US) for the DB ITT population. To derive the modified index episode, the manic index episode(s) with or without mixed features will be classified as manic episode(s); depressive index episode(s) with or without mixed features will be classified as depressive episode(s). Estimates of the hazard ratio (HR) and 95% confidence intervals will be based on the Cox proportional hazards model with treatment group as the covariate stratified by modified index episode (manic or depressive) and region (US, non-US). The Kaplan-Meier estimates for the cumulative distribution of the relapse rate for each treatment group will be provided.

Per the protocol, relapses are collected within a double-blind treatment period that lasts with a maximum of 39 weeks (or 273 days + 3 days visit time window), hence all survival analyses will censor data at 276 days.

The primary hypotheses for cariprazine 3.0 mg/d and 1.5 mg/d treatment groups versus placebo will be tested sequentially in order to control the overall Type I error rate. The comparison of cariprazine 3.0 mg/d versus placebo will be tested first at two-sided 0.05 significance level, and only when it is significant, the comparison of cariprazine 1.5 mg/d versus placebo will be tested also at the two-sided 0.05 significance level. This testing strategy controls the overall Type I error rate at 0.05 significance level.

Two sensitivity analyses will be performed to assess the robustness of the primary analysis results to the possible violation of the noninformative censoring assumption.

The first sensitivity analysis will be based on the delta-adjusted method examined by Zhao et al. (2014), which specifies that the hazard of having an event for subjects who discontinued before the time point is increased relative to the hazard for subjects who continued beyond the time point for the experimental treatment group. The delta-adjustment will be gradually increased from zero until reaching the tipping point when the statistical significance of the primary efficacy endpoint is overturned, and the plausibility of the magnitude of delta-adjustment needed for reaching the tipping point will be subject to clinical scrutiny.

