The second sensitivity analysis is an extension of the placebo-based pattern mixture model proposed by Lu (2014, 2015). The placebo-based pattern mixture model assumes that patients who discontinued from the cariprazine treatment groups would have disease progression after discontinuation similar to that of placebo. The extended placebo-based pattern mixture model uses a sensitivity parameter to characterize the gradual deviation from the noninformative censoring underlying the primary analysis toward the informative censoring underlying the placebo-based pattern mixture model. The extended placebo-based pattern mixture model sensitivity analysis for time-to-event data is described as follows:

Let $h_0(t)$ denote the baseline hazard function associated with the placebo group. Let β_1 and β_2 denote the treatment effects in terms of log HRs under noninformative censoring for cariprazine 1.5 mg/d versus placebo and cariprazine 3.0 mg/d versus placebo, respectively. The hazard functions associated with the cariprazine 1.5 and 3.0 mg/d groups under noninformative censoring are thus given by $h_1(t) = h_0(t) \exp(\beta_1)$ and $h_2(t) = h_0(t) \exp(\beta_2)$, respectively. Consider the extended placebo-based pattern mixture model sensitivity analysis. For the placebo group, we assume that patients with premature discontinuation would have comparable experience after discontinuation to their counterparts without premature discontinuation. For the cariprazine treatment groups, each dropout time point for cariprazine patients defines a missing data pattern, and we assume that patients with premature discontinuation would have disease progression after discontinuation somewhere between their counterparts without premature discontinuation and patients in the placebo group. Specifically, we assume that $h_1(t) = h_0(t) \exp((1-\phi)\beta_1)$ and $h_2(t) = h_0(t) \exp((1-\phi)\beta_2)$ for $t > C$, where C denotes the time of premature discontinuation. The sensitivity parameter $\phi \in [0,1]$ characterizes the gradual deviation from the noninformative censoring with $\phi = 0$ toward the informative censoring underlying the placebo based pattern mixture model with $\phi = 1$. A multiple imputation approach will be used to implement the extended placebo-based pattern mixture model.

Sample SAS programs for primary efficacy analysis and sensitivity analyses are provided in [Appendix I](#) and [Appendix II](#).

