APPENDIX I. SAS PROGRAM FOR PRIMARY EFFICACY ANALYSIS

The primary efficacy analysis for time to relapse include (1) the log-rank test and (2) the Cox proportional hazards model with treatment group and modified index episode (manic or depressive) as the covariate. The sample SAS code for these analyses are provided below. Note in the dataset adtte (DB ITT population), variables trt02pn and trt02p are for the double-blind treatment group, episode is for the modified index episode, aval is for the time (days) to censor/relapse, and cnsr is for the status of censored (=0) or relapsed (=1).

(1) SAS program for log-rank test comparing treatment groups trt02pn=0 and =1:

```
proc lifetest data=adtte method=km;
  strata episode region/test=logrank group=trt02p diff=control('Placebo');
  time aval * cnsr(0);
run;
```

(2) SAS program for Cox proportional hazard model:

```
proc phreg data=adtte;
  class trt02p (ref= 'Placebo') episode(ref='depressive') region;
  model aval * cnsr(0)= episode region trt02p/rl;
  contrast ' cariprazine 1.5 mg/d vs placebo Episode=depressive'    trt02p 1 0  episode 0/
estimate=exp e;
  contrast ' cariprazine 3.0 mg/d vs placebo Episode=depressive'    trt02p 0 1  episode 0/
estimate=exp e;
  contrast ' cariprazine 1.5 mg/d vs placebo Episode=manic'      trt02p 1 0  episode 1/ estimate=exp e;
  contrast ' cariprazine 3.0 mg/d vs placebo Episode=manic'      trt02p 0 1  episode 1/ estimate=exp e;
  ods output parameterestimates=pvval;
run;
```

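### The Appendix I Cox program is not the stratified model of SAP Section 10.1, and none of its four episode-labelled contrasts gives an episode-specific hazard ratio

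*SAP*

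**What the plan says.** Three descriptions of the Cox analysis for the primary endpoint differ.

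- **SAP Section 10.1** specifies a "Cox proportional hazards model with treatment group as the covariate stratified by modified index episode (manic or depressive) and region (US, non-US"). Protocol Section 7.3.1 also stratifies, but by episode only: "Cox proportional hazards model with treatment group as covariates stratified by modified index episode (manic or depressive").
- **The opening sentence of SAP Appendix I** describes a "Cox proportional hazards model with treatment group and modified index episode (manic or depressive) as the covariate". It mentions neither strata nor region.
- **The PHREG step in Appendix I** is "model aval * cnsr(0)= episode region trt02p/rl". Placebo and depressive are the reference levels. Episode and region enter as main effects, there is no STRATA statement, and there is no `trt02p*episode` term.

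The step then requests four contrasts, each dose against placebo for each episode type, for example "cariprazine 3.0 mg/d vs placebo Episode=depressive" and "cariprazine 3.0 mg/d vs placebo Episode=manic". The depressive pair puts coefficient 0 on episode and the manic pair puts coefficient 1. The only table saved is the parameter table ("ods output parameterestimates=pvval").

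The log-rank step in the same appendix is stratified by episode and region, as Section 10.1 says.

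**The concern.** Appendix I is the only coded specification of the primary HR in these documents. Appendix IV records that the appendix code was revised under SAP Amendment #3 to add region, yet the PHREG step still departs from Section 10.1.

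The contrasts matter more than the missing STRATA statement. A reader would take a line labelled manic as the effect of drug against placebo in manic-index patients. The model cannot estimate that, and the line as coded estimates something else. Efficacy by modified index episode is a planned subgroup analysis in Section 10.1, so the printed contrasts could be mistaken for it.

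**Working it through.** **What the contrasts estimate.** With reference coding, the fitted model is

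log h(t) = log h0(t) + g·manic + r·region + b1·(1.5 mg/d) + b2·(3.0 mg/d).

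- Depressive contrasts: exp(b1) and exp(b2), the single HR per dose that applies to both episode types.
- Manic contrasts: exp(b1 + g) and exp(b2 + g), the drug HR times the manic-to-depressive HR.
- Drug against placebo within manic-index patients in this model is again exp(b1) or exp(b2), because g cancels.

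**Inputs.** From SAP Section 14.0: HR 0.42, placebo relapse 35% at Week 39, 26% dropout, 126 patients per arm. Assumed, because the documents give no figures: an episode HR of 0.5 to 2.0, exponential times, 50/50 splits by episode and region, and no region effect.

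**Check of the set-up against the plan.** Over 39 weeks the cumulative hazards are −ln 0.65 = 0.431 for placebo relapse, 0.42 × 0.431 = 0.181 for relapse on cariprazine, and −ln 0.74 = 0.301 for dropout. The probability of an observed relapse is H/(H + D) × (1 − exp(−(H + D))).

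- Placebo: 126 × 0.3055 = 38.5 events.
- Each cariprazine arm: 126 × 0.1436 = 18.1 events.
- Total: 38.5 + 2 × 18.1 = 74.7, in line with the plan's figure of about 75.

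**Manic contrasts.** The target is 0.42 × episode HR. The table shows 1000 simulated trials per row for 3.0 mg/d, with a true drug HR of 0.42 in both episode types.

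| Episode HR | Target | Median estimate | 95% CI contains 0.42: manic contrast | 95% CI contains 0.42: treatment row |
|---|---|---|---|---|
| 0.5 | 0.21 | 0.204 | 53% | 96% |
| 0.7 | 0.29 | 0.290 | 84% | 95% |
| 1.0 | 0.42 | 0.427 | 95% | 95% |
| 1.4 | 0.59 | 0.580 | 84% | 94% |
| 2.0 | 0.84 | 0.846 | 53% | 95% |

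A hand check agrees. The mean standard error of the manic contrast was 0.373 to 0.383. At episode HR 0.7 the shift is |ln 0.7|/0.378 = 0.94 standard errors, so coverage is about Φ(1.96 − 0.94) − Φ(−1.96 − 0.94) = 0.84. With a 30/70 or 70/30 episode split, at episode HR 0.7 and 1.4, coverage was 84% to 87%.

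**Depressive contrasts.** These mislead only if the drug effect differs by episode. The HRs here are assumed.

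- 0.30 manic, 0.60 depressive: median 0.45 against a true 0.60, with the CI containing the truth in 82% of trials.
- 0.60 manic, 0.30 depressive: median 0.45 against a true 0.30, with the CI containing the truth in 70%.
- A stratified model with `trt02p*episode` recovered both HRs with 94% to 96% coverage.

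**Covariate versus stratified adjustment, main HR.** The absolute difference had a median of 0.004, a 95th percentile of 0.016 to 0.019 and a maximum of 0.09. With strongly non-proportional baselines by episode (Weibull shapes 0.5 and 2, 400 trials per setting), the median was 0.008 to 0.009 and the 95th percentile 0.025.

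**The case against.** The programs are samples: Section 10.1 says "Sample SAS programs for primary efficacy analysis and sensitivity analyses are provided in" the two appendices. The text of Section 10.1 is clear, does not ask for the contrasts, and already plans the analysis within each episode category. Only the parameter table is saved. Under the fitted model the common HR is what the model implies for depressive-index patients, so only the manic pair is miscoded. The episode HR is assumed, and stratified versus covariate adjustment hardly moves the main HR.

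Most of this stands, and it limits the point to a minor one. It does not remove it. The code conflicts with the text it is meant to implement, and it prints two HRs that are wrong for their labels unless the episode HR is 1. The depressive lines are correct under the model's own assumption, but their labels promise an episode-specific estimate that the model cannot give. The table specifications are in a separate document, so whether the contrasts would be reported cannot be settled here.

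There is also a fair objection to the correction. Adding region as a stratum follows the SAP but not Protocol Section 7.3.1. The change is recorded in Appendix IV, but SAP Section 18, which lists changes from the protocol, omits it.

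**Conclusion.** The point holds and is minor. The mismatch between text and code, and the meaning of the four contrasts, follow from the code by algebra and need no assumption. The size of the manic error does rest on one: with a drug HR of 0.42 and an assumed episode HR of 0.5 to 2.0, those contrasts target 0.21 to 0.84, and their confidence intervals contain 0.42 in as few as 53% of trials. The contrast error does not touch the stratified log-rank p-values, the order of testing (3.0 then 1.5 mg/d) or the treatment rows of the saved parameter table. Replacing strata by covariates has almost no effect on the main HR under the conditions tried.

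**What to change.** In Appendix I, before unblinding:

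1. Confirm the event coding of the analysis dataset. Appendix I says `cnsr` = 0 means censored, while Appendix II treats `cnsr` = 0 as the event.
2. Use `class trt02p(ref='Placebo'); model aval*cnsr(0)=trt02p/rl; strata episode region;` and adapt the censoring value if step 1 requires it.
3. Delete all four contrasts. Take episode-specific HRs from the subgroup analysis in Section 10.1, or from a stratified model with `trt02p*episode`.
4. Reword the opening sentence so that treatment is the only covariate and episode and region are strata.
5. Add region as a stratification factor to the list in SAP Section 18.

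The cost is one PHREG step, one sentence and one line in Section 18. It needs no extra data and leaves the primary test unchanged.

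The Cox fits after imputation in Appendix II also lack a STRATA statement and omit region. Align them only as part of a separate and larger correction of that program, which is not costed here. Its imputation steps use `exp(treated*...)` with `treated` coded 1 and 2. At a drug HR of 0.42 and no adjustment, the hazard multipliers become 0.42 for placebo and 0.42² = 0.18 for cariprazine, instead of 1 and 0.42.

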APPENDIX II. SAS PROGRAM FOR SENSITIVITY ANALYSES I AND II

The SAS program for Sensitivity Analyses II (delta-adjusted method) and III (placebo based pattern-mixed model) are presented as below. Note the program is for comparison of two treatment groups (eg. Dose1 vs. placebo):

```
*****
Name:           Sensi.sas
Date:           18April2019
Description:    This analysis program performs the below sensitivity analyses for the primary Efficacy parameter (time to relapse):
1. Delta-adjusted method (Zhao 2014)
2. Placebo-based pattern mixture model (Lu, 2014 and 2015)

Datasets used: (Note: This SAS program is for comparison between two treatment groups.) ads1(AdaM), with the below variables:
Variable      Type   Len   Format      Informat   Label
-----
AP02EDT      Num    8     YYMMDD10.      Period 02 End Date - DB
AP02SDT      Num    8     YYMMDD10.      Period 02 Start Date - DB
-
EOPH3STT     Char   20
ITTDDBFL     Char   1
RANDDT       Num    8     YYMMDD10.      Date of Randomization
SUBJID       Char   20
RELAPSE      Char   8
EPISODE      Char   20
                           $7.      Subject Identifier for the Study
                           Relapse event
                           Index episode

adtte(AdaM), with the below variables:
Variable      Type   Len   Format      Informat   Label
-----
AVAL          Num    8
CNSR          Num    8
PARAMN        Num    8
SUBJID       Char   20
TRTO2PN      Num    8
EPISODE      Char   20
                           $7.      Analysis Value, time to event
                           Censor
                           Parameter (N)
                           Subject Identifier for the Study
                           Planned Treatment for DB
                           Index episode

Macro(s) called: (none)
Output files:   (none)
Revision:
*****
libname ad '/sasdata/rgh/rgh25';

%let fllow=39; ***planned minimum follow-up time***;
%let flhigh=39; ***planned maximum follow-up time***;

* obtain the planned follow-up time for each subject;

data a1;
set ads.adsl(keep=subjid randdt tr02sdt tr02edt eoph3stt relapse ittdbfl episode region
where=(ittdbfl='Y'));
durdb=tr02edt-randdt+1;
if index(upcase(EOPH3STT), 'COMPLETE')>0 then COMPDBFL="Y";
else COMPDBFL="N";
run;

proc freq data=a1;
  tables compdbfl*eoph3stt/list missing;      *patient disposition status;
run;

proc univariate data=a1 noprint;
  where COMPDBFL="N";
  var durdb;
  output out=b1 max=maxdurb;  *max duration for discontinued;
run;
```

```

proc sort data=a1 out=a2;
  by randdt;
run;

data b2;
  set a2 end=eof;
  retain franddt;
  format franddt yymmdd10.;
  if _n_=1 then do;
    franddt = randdt;
    set b1;
  end;
  if eof then do;
    lranddt = randdt;
    ta = lranddt - franddt; * duration of enrollment period;
    tfmin = %eval(&fllow.*7);
    tfmax = %eval(&fhigh.*7);
    output;
  end;
  keep franddt ta tfmin tfmax;
  label franddt="Randomization Date for First Randomized Subject"
    ta="Duration of Enrollment Period (days)"
    tfmin="Minimum Follow-up Time (days)"
    tfmax="Maximum Follow-up Time (days)";
run;

proc print data=b2 label;
  var franddt ta tfmin tfmax;
run;

data a3;
  set a1;
  if _n_=1 then set b2;
  e = randdt - franddt; * enrollment time for the current subject;
  *if compynfl="Y" or index(upcase(trmspc),"26 WEEK")>0 then do; /* completed the study */
  if compdbfl="Y" then do;
    tf = durdb;
    complete=1;
  end;
  else do; * relapsed or discontinued for other reasons;
    tf = min(ta - e + tfmin, tfmax);
    complete=0;
  end;
run;

data raw1;
  merge a3
    ad.adtte(keep=aval cnsr paramn subjid trt03pn where=(paramn=0)); ***paramn=0 corresponds
  to time to relapse***;
  by subjid;
  status=(cnsr=0);
  rename subjid=subj trt03pn=treated aval=time tf=followup;
  keep subjid trt03pn cnsr status aval complete tf episode;
run;

* check number of events per treatment group;
proc freq data=raw1;
  tables treated*status/norow nocol nopercents;
run;

ods listing close;

* examine Bayesian analysis results to determine thinning;
proc phreg data=raw1;
  class episode;
  model time*status(0)=episode region treated;
  bayes piecewise=hazard;
run;

* ==> thin=10 is enough to achieve approx. indep. posterior samples;
%let thin=10; * thinning;
%let ninterval=8; * number of time intervals for piecewise exponential;
%let nimps=200; * number of imputations;
%let seed=314;

```

```

* obtain sample size in raw data;
proc sql noprint;
    select count(*) into :n from raw1;
quit;

data raw;
    set raw1(drop=subj);
    subj = _n_;
run;

options nonotes nosource;
ods noreresults;
ods html close;
ods graphics off;

data bootid;      * dummy data set to store bootstrapped subject numbers;
    seed=123;
    do boot=0 to 100;
        do i=1 to &n;
            if boot=0 then subj=i;
            else do;
                call ranuni(seed, u);
                subj=ceil(&n*u); * bootstrapped subject number;
            end;
            output;
        end;
    end;
    call symput("seed", strip(put(seed,12.)));
    keep boot subj;
run;

* match the subject number to retrieve other subject-specific data;
proc sql noprint;
    create table bootsamp as
    select b.boot, a.subj, a.treated, a.followup, a.time, a.status a.complete a.episode
    from raw as a, bootid as b
    where a.subj=b.subj
    order by boot, subj;
quit;

* obtain posterior draws of model parameters from bootstrap samples;
proc phreg data=bootsamp;
    by boot;
    class episode region treated(ref='1');
    model time*status(0)=episode region treated;
    bayes nmc=%eval(&nimps*&thin) piecewise=hazard seed=314;
    ods output Partition=partition PosteriorSample=postsamp;
run;
ods output close;

* Boot samp data for both treatments
data bootsamp1;
set bootsamp;
if treated in (1,2); * Placebo Vs 1.5mg;
run;

data bootsamp2;
set bootsamp;
if treated in (1,3); * Placebo Vs 3.0;
if treated=3 then treated=2;
run;

/*Delta-Adjusted Method*/
%macro delta(postsamp=, bootsamp=, trt=, dataout=);

data postsam2;
    set &postsamp.;
    temp = (Iteration - 2000 - 1)/&thin + 1;
    _imputa_ = floor(temp);
    if _imputa_ = temp;
    rename &trt.=beta;
    keep boot _imputa_ lambda1-lambda&ninterval &trt.;
run;

```

```

*merge with raw data;
proc sql noprint;
    create table raw2 as
        select a.* , b.subj, b.treated, b.followup, b.time, b.status, b.complete, b.episode
        from postsam2 as a, &bootsamp. as b
        where a.boot=b.boot
        order by boot, _imputa_, subj;
quit;

* obtain maximum follow-up;
proc univariate data=&bootsamp. noprint;
    by boot;
    var time;
    output out=maxtime max=maxtime; * maximum survival time;
run;

* organize partition information;
proc transpose data=partitit out=partitit(drop=_name_ _label_)
    prefix=a;
    by boot;
    var UpperTime;
run;

data partitit;
    merge partitit maxtime;
    by boot;
    a&ninterval = maxtime+1; * a large number to represent infinity;
    drop maxtime;
run;

data raw2;
    merge raw2 partitit;
    by boot;
run;

* impute censored event times for early dropouts;
data raw4;
    set raw2 end=eof;
    if _n_=1 then seed=789;
    retain seed;

    array a{&ninterval};
    array lambda{&ninterval};

    call ranuni(seed, u);
    do delta=0 to 2 by 0.147;
    nlogu = -log(u)/exp(treated*(beta+delta)); * MNAR;

    * no imputation needed for subjects with events or for completers;
    if status=1 or (status=0 and time=followup) then do;
        time3 = time;
        status3 = status;
    end;
    else do; * impute censored event time;
        * locate the time interval that contains the censoring time;
        j1 = 1;
        do while (time >= a[j1]);
            j1 = j1 + 1;
        end;

        * locate the time interval containing the censored event time;
        * cumulative hazard in the first interval;
        v = lambda[j1]*(a[j1] - time);
        j2 = j1;
        do while (nlogu > v and j2 < &ninterval);
            j2 = j2 + 1; * cumulative hazard in current interval;
            v = v + lambda[j2]*(a[j2] - a[j2-1]);
        end;

        * obtain the event time;
        if j2 = j1 then
            u3 = nlogu/lambda[j1] + time; * event in interval j1;
        else
            u3 = a[j2] - (v - nlogu)/lambda[j2]; * event in interval j2;
    end;

```

```

time3 = min(u3, followup);
status3 = (u3 <= followup);
end;
output;
end;

if eof then call symput("seed", strip(put(seed,12.)));
keep boot _imputa_ subj episode treated delta time3 status3;
run;

proc sort data=raw4;
  by boot _imputa_ delta;
run;

* perform log-rank test for each imputed data set;
proc lifetest data=raw4;
  by boot _imputa_ delta;
  time time3*status3(0);
  strata episode region /test=logrank group=treated;
  ods output HomStats=lrdiff2 LogrankHomCov=vlrdiff2;
run;
ods output close;

data vlrdiff2;
set vlrdiff2;
new=input(treated, 8.);
drop treated;
rename new=treated;
run;

* combine numerator and denominator of the log-rank test;
data lrtest2;
  merge lrdiff2(where=(treated=1)) vlrdiff2(where=(treated=1));
  by boot _imputa_ delta;
  stderr = sqrt(_1); * standard error of log-rank test statistic;
run;

proc sort data=lrtest2;
  by boot delta _imputa_;
run;

* use Rubin rule to make multiple imputation inference based on log-rank test;
proc mianalyze data=lrtest2;
  by boot delta;
  modeleffects logrank ;
  stderr stderr;
  ods output ParameterEstimates=mlrtes2;
run;
ods output close;

* fit Cox model to each imputed data set;
proc phreg data=raw4;
  class episode;
  by boot _imputa_ delta;
  model time3*status3(0)=episode treated;
  ods output ParameterEstimates=phest2;
run;
ods output close;

proc sort data=phest2;
  by boot delta _imputa_;
run;

* use Rubin rule to make multiple imputation inference based on Cox model;
proc mianalyze data=phest2(where=(parameter="treated"));
  by boot delta;
  modeleffects estimate;
  stderr stderr;
  ods output ParameterEstimates=miphest2;
run;
ods output close;

data miout2a;
  merge mlrtes2(keep=boot delta probt)
        miphest2(keep=boot delta estimate stderr lclmean uclmean);

```

```

by boot delta;
plogrank = probt;
hazardra = exp(estimate);
hrlowerc = exp(lclmean);
hrupperc = exp(uclmean);
*drop probt estimate lclmean uclmean;
run;

proc sort data=miout2a out=miout2b;
  by delta boot;
  where boot>0;
run;

proc univariate data=miout2b nopolish;
  by delta;
  var estimate;
  output out=miout2c std=StdErrbo;
run;

data miout2;
  merge miout2a(where=(boot=0)) miout2c;
  by delta;
  bhrlower = exp(estimate - 1.96*stderrbo);
  bhrupper = exp(estimate + 1.96*stderrbo);
  label stderrbo=" ";
run;

data &dataout.;
  format Analysis $20.;
  set miout2(in=b);
  analysis="Sensitivity";
  drop boot probt lclmean uclmean;
  format estimate stderr stderrbo bhrlower bhrupper 8.3;
run;

%mend;

%delta(postsamp=postsamp, bootsamp=bootsamp1, trt=treated2, dataout=sensi3);
%delta(postsamp=postsamp, bootsamp=bootsamp2, trt=treated3, dataout=sensi4);

* /*placebo-based pattern mixture model*/
%macro pattern(postsamp=, bootsamp=, trt=, dataout=);*;

data postsam2;
  set &postsamp.;
  *set postsamp;
  temp = (iteration - 2000 - 1)/&thin + 1;
  _imputa_ = floor(temp);
  if _imputa_ = temp;
  rename &trt.=beta;
  *rename treated2=beta;
  keep boot _imputa_ lambda1-lambda&ninterval &trt.;
run;

* merge with raw data;
proc sql nopolish;
  create table raw2 as
  select a.*, b.subj, b.treated, b.followup, b.time, b.status, b.episode
  from postsam2 as a, &bootsamp. as b
  where a.boot=b.boot
  order by boot, _imputa_, subj;
quit;

* obtain maximum follow-up;
proc univariate data=&bootsamp. nopolish;
  by boot;
  var time;
  output out=maxtime max=maxtime; * maximum survival time;
run;

* organize partition information;
proc transpose data=partitio out=partitit(drop=_name_ _label_) prefix=a;
  by boot;
  var uppertime;
run;

```

```

data partitit;
  merge partitit maxtime;
  by boot;
  a&ninterval = maxtime+1;  * a large number to represent infinity;
  drop maxtime;
run;

data raw2;
  merge raw2 partitit;
  by boot;
run;

* impute censored event times for early dropouts;
data raw3;
  set raw2 end=eof;
  if _n_=1 then seed=789;
  retain seed;

  array a{&ninterval};
  array lambda{&ninterval};

  call ranuni(seed, u);
  do phi=0 to 1 by 0.2;
  nlogu = -log(u)/exp(treated*(1-phi)*beta ); * MNAR;

  * no imputation needed for subjects with events or for completers;
  if status=1 or (status=0 and time=followup) then do;
    time3 = time;
    status3 = status;
  end;
  else do; * impute censored event time;
    * locate the time interval that contains the censoring time;
    j1 = 1;
    do while (time >= a[j1]);
      j1 = j1 + 1;
    end;

    * locate the time interval containing the censored event time;
    * cumulative hazard in the first interval;
    v = lambda[j1]*(a[j1] - time);
    j2 = j1;
    do while (nlogu > v and j2 < &ninterval);
      j2 = j2 + 1;  * cumulative hazard in current interval;
      v = v + lambda[j2]*(a[j2] - a[j2-1]);
    end;

    * obtain the event time;
    if j2 = j1 then
      u3 = nlogu/lambda[j1] + time; * event in interval j1;
    else
      u3 = a[j2] - (v - nlogu)/lambda[j2]; * event in interval j2;

    time3 = min(u3, followup);
    status3 = (u3 <= followup);
  end;
  output;
end;

if eof then call symput("seed", strip(put(seed,12.)));
keep boot _imputa_ subj treated phi time3 status3 episode;
run;

proc sort data=raw3;
  by boot _imputa_ phi;
run;

* perform log-rank test for each imputed data set;
proc lifetest data=raw3;
  by boot _imputa_ phi;
  time time3*status3(0);
  strata episode region /test=logrank group=treated;
  ods output HomStats=lrdiff LogrankHomCov=vldiff;
run;

```

```

data vlrldiff;
set vlrldiff;
new=input(treated, 8.);
drop treated;
rename new=treated;
run;

* combine numerator and denominator of the log-rank test;
data lrtest1;
  merge lrdiff(where=(treated=1)) vlrldiff(where=(treated=1));
  by boot _imputa_ phi;
  stderr = sqrt(_1); * standard error of log-rank test statistic;
run;

proc sort data=lrtest1;
  by boot phi _imputa_;
run;

* use Rubin rule to make multiple imputation inference based on log-rank test;
proc mianalyze data=lrtest1;
  by boot phi;
  modeleffects logrank ;
  stderr stderr;
  ods output ParameterEstimates=milrtest;
run;

* fit Cox model to each imputed data set;
proc phreg data=raw3;
  class episode;
  by boot _imputa_ phi;
  model time3*status3(0)=episode treated;
  ods output ParameterEstimates=phest1;
run;

proc sort data=phest1;
  by boot phi _imputa_;
run;

* use Rubin rule to make multiple imputation inference based on Cox model;
proc mianalyze data=phest1(where=(Parameter="treated"));
  by boot phi;
  modeleffects estimate ;
  stderr stderr;
  ods output ParameterEstimates=miphest;
run;

data mioutla;
  merge milrtest(keep=boot phi probt)
        miphest(keep=boot phi estimate stderr lclmean uclmean);
  by boot phi;
  plogrank = probt;
  hazardra = exp(estimate);
  hrlowerc = exp(lclmean);
  hrupperc = exp(uclmean);
  *drop probt estimate lclmean uclmean;
run;

proc sort data=mioutla out=miout1b;
  by phi boot;
  where boot>0;
run;

proc univariate data=miout1b noprint;
  by phi;
  var estimate;
  output out=miout1c std=StdErrbo;
run;

data miout1;
  merge mioutla(where=(boot=0)) miout1c;
  by phi;
  bhrlower = exp(estimate - 1.96*stderrbo);
  bhrupper = exp(estimate + 1.96*stderrbo);
  label stderrbo=" ";
run;

```

```

data &dataout.;
  format Analysis $20.;
  set miout1(in=b);
  Analysis="Sensitivity";
  drop boot probt lclmean uclmean;
  format estimate stderr stderrbo bhrlower bhrupper 8.3;
run;

%mend;

/*Placebo Vs 3.0mg/day*/
%pattern(postsamp=postsamp, bootsamp=bootsamp1, trt=treated2, dataout=sensi1);
/*Placebo Vs 1.5mg/day*/
%pattern(postsamp=postsamp, bootsamp=bootsamp2, trt=treated3, dataout=sensi2);

data placebo;
  set sensi1(in=a) sensi2(in=b);
  if a then compare="Placebo Vs Cariprazine 1.5mg/day";
  if b then compare="Placebo Vs Cariprazine 3.0mg/day";
run;

title 'Placebo-based pattern mixture model (Lu, 2014, 2015)';
proc print data=placebo label;
  var analysis phi plogrank hazardra hrlowerc hrupperc;
  format plogrank 6.4;
run;

data delta;
  set sensi3(in=a) sensi4(in=b);
  if a then compare="Placebo Vs Cariprazine 1.5mg/day";
  if b then compare="Placebo Vs Cariprazine 3.0mg/day";
run;

title 'Delta-adjusted Method (Zhao, 2014)';
proc print data=delta label;
  var analysis delta plogrank hazardra hrlowerc hrupperc;
  format plogrank 6.4;
run;

```

